2.15.3 Study Design (REFER TO APPENDIX D)

The study is intended to determine the difference in efficacy and safety between the device arm and control arm (subjects treated with OMT).

The ACP clinical trial is an adaptive design with interim sample size analyses that use current data and project the necessary sample size and follow-up time based upon observed efficacy and safety event rates in the device and control subjects.

Three primary endpoints and hypotheses are being evaluated in the ACP clinical trial

1. An efficacy endpoint which compares the 2-year event rates of ischemic stroke and peripheral thromboembolism. This is a non-inferiority analysis where the device will be deemed efficacious if the risk ratio is < 1.75 or the risk difference in two years event rates is < 2.87 .
2. A long-term safety endpoint which compares long-term composite rates of all-cause mortality and major bleed. This is a superiority analysis where the device will be deemed safe if the safety event rate in the device arm is proven superior to the safety event rate in the control arm (OMT).
3. An acute safety (short-term) endpoint which compares the rate of device or procedure related serious adverse events against a performance goal (PG). If this

rate is less than 5%, the device is considered to have met the acute safety endpoint.

The primary efficacy and primary long-term safety hypotheses are included in the adaptive design. The study will accrue subjects until there is high predictive probability that the sample size is sufficient to meet the efficacy and long term safety endpoints or until it is evident that in spite of enrolling to the maximum sample size it is unlikely to meet the efficacy and long-term safety endpoints.

The analysis for the primary acute safety endpoint will be performed on the entire sample size as determined by the adaptive design governed by the efficacy and long term safety endpoints.

The ACP clinical trial is powered to concurrently prove the non-inferiority efficacy endpoint, along with the acute and long-term safety endpoints. The precise follow-up time may vary in this adaptive design.

Interim sample size analyses will be performed when 400 subjects are enrolled, then again every 50 subjects until a possible maximum of 3000 subjects are obtained. Once subject accrual is stopped and the predictive probability of trial success for both efficacy and long-term safety is high, all subjects will be followed for at least 6 months.

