2.15.3.2 Primary Effectiveness Endpoint and Hypothesis

The primary effectiveness endpoint for the ACP study is the two-year annualized rate of ischemic stroke and peripheral thromboembolism. The rate will be calculated in each treatment arm using a piecewise exponential model (non-constant hazard rate) and assessing the number of primary endpoint events divided by the number of subject-years of follow-up within each timeframe. The 2-year event rate is then found by the product of not having an event during each segment. For subjects who have already experienced an endpoint, additional endpoints or follow-up time will not be factored into

this calculation. If a subject experiences a non-fatal safety event, he or she is still tracked for efficacy events.

Separate estimates will be performed for the posterior probability distributions for the two-year event rate in the subjects randomized to the device arm and for the two-year event rate for subjects randomized to the control arm. Once these estimates are obtained, the posterior probability distributions for both the risk ratio (device rate / control rate) and risk difference (device rate minus control rate) will be calculated.

Non-inferiority criterion will be considered met if either the hazard ratio of device to control rate is significantly less than 1.75, or if the risk difference is less than 2.87 percentage points.

Let π_{DEVICE} be the primary effectiveness endpoint rate in the device arm, while π_{CONTROL} is the corresponding rate in the control arm. Specifically, the following null and alternative hypotheses will be tested:

$$H_0: \pi_{\text{DEVICE}} / \pi_{\text{CONTROL}} \geq 1.75$$

$$H_a: \pi_{\text{DEVICE}} / \pi_{\text{CONTROL}} < 1.75$$

where π_{DEVICE} equals the two-year event rate in the device arm and π_{CONTROL} equals the two-year efficacy event rate in the control arm. The null hypothesis will be rejected and non-inferiority to OMT will be concluded if the upper bound of the two-sided 97.6% Bayesian confidence interval for the ratio between the device rate and control rate is less than 1.75. This is equivalent to testing whether the posterior probability, $\Pr(\pi_{\text{DEVICE}} / \pi_{\text{CONTROL}} \geq 1.75) > 0.988$.

For the Risk Difference, the following hypotheses will be tested.

$$H_0: \pi_{\text{DEVICE}} - \pi_{\text{CONTROL}} \geq 2.87\%$$

$$H_a: \pi_{\text{DEVICE}} - \pi_{\text{CONTROL}} < 2.87\%$$

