The null hypothesis will be rejected and non-inferiority to OMT will be concluded if the upper bound of the two-sided 97.6% Bayesian confidence interval for the difference between the two-year device rate and two-year control rate is less than 2.87%. This is equivalent to testing whether the posterior probability, $\Pr(\pi_{\text{DEVICE}} / \pi_{\text{CONTROL}} \geq 1.75) > 0.988$.

97.6% confidence intervals are used so that the Type I error for the composite hypothesis test is not above a one-sided 2.5%.

With this combination of allowable risk ratio (1.75) and risk difference (2.87%) the Type I error rate is highest at $\pi_{\text{CONTROL}} = 3.82\%$ and $\pi_{\text{DEVICE}} = 6.69\%$ -- the point where $\pi_{\text{DEVICE}} /$

$\pi_{\text{CONTROL}} = 1.75$ and $\pi_{\text{DEVICE}} - \pi_{\text{CONTROL}} = 2.87\%$. The type I error rate for this scenario is shown in **Table 5**.

If the device endpoint rate is shown to be successful for non-inferiority to control, it will then be tested for superiority. In that event, the following null and alternative hypotheses will be tested:

$$\begin{aligned} H_0: \pi_{\text{DEVICE}} - \pi_{\text{CONTROL}} &\geq 0 \\ H_a: \pi_{\text{DEVICE}} - \pi_{\text{CONTROL}} &< 0 \end{aligned}$$

While the above hypotheses are stated as a subtraction of rates, it is equivalent to testing whether the ratio of the rates is lower than 1.0.

The following describes the Bayesian adaptive design for the primary efficacy endpoint. This design was created by Berry Consultants, (Austin, Texas) using the specific model assumptions for this trial.

The two-year event rates are calculated using a piecewise exponential model that recognizes that event rates may change during the course of subject follow-up.

The control arm uses a 7-piece model while the device arm uses an 8-piece model as described below:

Time intervals for the control arm:

- Day 0- Day 6
- Day 7- Day 30
- Day31- Day 60
- Day 61- 6 months
- 6 months-12 months
- 12 months -18 months
- 18 months-24 months

Time intervals for the device arm:

- Day 0 (randomization) to Day before Procedure Day (the procedure must occur by 14-days after randomization)
- Procedure Day to Procedure Day + 6 days
- Procedure Day + 7 days to Day 30
- Day 31- Day 60
- Day 61- 6 months
- 6 months -12 months
- 12 months-18 months
- 18 months-24 months

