2.15.3.4 Primary Safety Endpoints and Hypotheses

The **primary safety endpoint** for the ACP study has two components: acute safety and long-term safety.

- a. Acute safety consists of procedure related serious adverse events that qualify as one of the following:
 - procedure-related death (i.e., death occurring during the implantation procedure).
 - pericardial effusion requiring treatment.
 - device embolization.
 - access site-related bleeding requiring transfusion ≥ 2 units.
 - damage to other cardiac or major non-cardiac cardiovascular structures

The acute analysis does not inform the adaptive design in that its probability of success does not affect the adaptive sample size algorithm.

In the acute safety analysis, the rate of device or procedure related serious adverse events from the time of randomization until hospital discharge is compared against a performance goal (PG) of 5.0% chosen from the literature.

Let π_{DEVICE} be this pre-discharge event rate in the device arm. Specifically, the following null and alternative hypotheses will be tested:

$$H_0: \pi_{\text{DEVICE}} \geq (\text{PG} = 5.0\%)$$

$$H_a: \pi_{\text{DEVICE}} < (\text{PG} = 5.0\%)$$

The null hypothesis will be rejected and the performance goal will be considered met if the upper bound of the one-sided confidence interval for the device rate is less than 5.0%.

- b. Long-term safety events can occur in either the device arm or the control arm and consist of the following:
 1. All-cause death; or
 2. Major bleeding defined as:
 - a. Symptomatic intracerebral or intraventricular hemorrhage; or subdural, subarachnoid, epidural, or ocular hemorrhage; or
 - b. Major non-cerebral bleed-defined as transfusion requiring ≥ 2 units, hospitalization requiring any transfusion or surgical or percutaneous interventional procedure to treat bleeding

Note: procedure-related pericardial effusions requiring treatment will not be counted as a major non-cerebral bleed

Subjects who experience a non-fatal efficacy event are still followed and included in the safety analysis.

The long-term safety analysis is a two-arm analysis that compares the safety events defined above between the device and the control arm. For both the device arm and the control arm, the events will be evaluated from the time of randomization until two years. This analysis will test for superiority of the device arm versus the control arm.

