2.15.3.6 Predictive Probability Calculations

The predictive probabilities of meeting the non-inferiority efficacy goal and superiority safety goal are calculated at each interim analysis as described in sections 2.15.3.3 and 2.15.3.5. Likewise the joint predictive probability of achieving the efficacy and safety goals are calculated assuming accrual stops at the current sample size and if it continues to the maximum sample size.

$P_{n,n}$ is the predictive probability of demonstrating non-inferiority (via the risk ratio OR the risk difference) for efficacy AND superiority for long-term safety if the study stops accruing subjects and wait for 24 months to perform the final analysis.

By continuing to enroll from the current sample size n subjects to the 3000 subject maximum, and then tracking all subjects another 2-years, , the predictive probability $P_{n,3000}$ of demonstrating non-inferiority (via the risk ratio OR the risk difference) for efficacy AND superiority for long-term safety can be calculated.

If $P_{n,n}$ is large, then there is a high probability that stopping accrual and following subjects for an additional two years will result in a final analysis that demonstrates sufficient efficacy and long-term safety. If $P_{n,n} \geq S_n$ (as shown in **Table 1**) then the DSMB and/or CEC is informed that the algorithm indicates that accrual should stop.

If $P_{n,3000} < F_n$, then there is a small chance of trial success even if the study runs to its maximum sample size and again the DSMB/CEC will be informed that the algorithm indicates that the trial should stop for futility. The subjects will be informed of this circumstance and enrollment will end. Enrolled subjects will be followed for a total of additional two years.

If $F_n \leq P_{n,3000}$ and $P_{n,n} > S_n$, the enrolling of subjects continues. Another sample size re-estimation will be performed once another 50 subjects are enrolled. Sample size analyses continue every 50 subjects until $P_{n,n} \geq S_n$, or $P_{n,3000} < F_n$, or the maximum number of subjects,3000, is reached.

If $P_{\underline{n},\underline{n}} > S_{\underline{n}}$ or the maximum number of subjects is obtained, analyses will be performed every 6 months as described in the previous section up to 24 months after the date the last patient is enrolled.

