2.15.5.2 Primary Safety

2.15.5.2.1 Procedural (Acute) Safety- This analysis compares the rate of procedure related serious adverse events (SAE) as listed below, that occur in the device arm from the time of randomization until hospital discharge to a performance goal (PG) chosen from the literature. The endpoint will be considered met if the 96% credible interval for the in-hospital event rate is entirely less than the PG.

- procedure-related death (i.e., death occurring during the implantation procedure).
- pericardial effusion requiring treatment.
- device embolization.
- access site-related bleeding requiring transfusion ≥ 2 units.
- damage to other cardiac or major non-cardiac cardiovascular structures

A literature search was conducted in order to establish a PG. The search criteria included catheter ablation for atrial fibrillation. This criterion was chosen because catheter ablation utilizes transseptal puncture to access the left atrium which is the common technique used to access the left atrial appendage and implant the ACP device. The search included electrophysiologic (EP) studies and summaries of safety and effectiveness (SSED).

In all, 29 sources (27 published articles and two SSEDs) were examined for reported complications of procedure related SAE (as listed above). Serious Adverse Events of procedure-related death (i.e., death occurring

during the implantation procedure), access site-related bleeding requiring transfusion ≥ 2 units and device embolization was clearly reported. The Atritech SSED served to provide an estimate of the rate for device embolization since the EP literature would lack this complication. However, in order to categorize literature reported complication against 'pericardial effusion requiring treatment' and 'Damage to other cardiac or major non-cardiac cardiovascular structures' the following criteria were used:

- Pericardial effusion requiring treatment included pericardial effusions that required pericardiocentesis and cardiac tamponade. Also included within this category are pericardial effusions that were medically treated, or where treatment was not specified. Please note this category does not include effusions that were spontaneously resolved.

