- Damage to other cardiac or major non-cardiac cardiovascular structures included serious complications requiring more than conservative medical attention such as pleural effusion, pneumo- or hemothorax, lung injury, pulmonary edema, valve damage, vascular injury including arteriovenous fistulae requiring surgical intervention, aortic dissection, aortic root puncture and coronary sinus perforation.

The average weighted complication rate derived from literature Meta-analysis is provided in **Table 3**.

Table 3- Performance Goal

Death (procedure-related)	Device Embolization	Access Site Bleeding (requiring ≥ 2 units)	Damage to Other Cardiac or Major Non-Cardiac Cardiovascular Structures	Pericardial Effusion (requiring treatment)
0.05%	0.22 %	2.97%	0.46%	1.23%
Average Weighted Complication Rate= 4.93%				

Therefore a performance goal of 5% is being established, against which the acute safety profile of the ACP device will be compared. A performance goal of 5% provides confidence that it adequately represents a threshold between event rates observed in literature and is clinically relevant. The ACP trial will meet its acute safety success if the two-sided 95% credible interval lies entirely below this PG.

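### Do the reversed non-inferiority probability, the reversed accrual sign and the differing acute-safety criteria leave the trial's decision rules undefined?

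*Combined protocol and SAP*

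**What the plan says.** **Effectiveness (section 2.15.3.2).** The null is a device-to-control ratio of 1.75 or more. It is rejected when the "upper bound of the two-sided 97.6% Bayesian confidence interval for the ratio between the device rate and control rate is less than 1.75". The next sentence restates this in posterior-probability form: "This is equivalent to testing whether the posterior probability, $\Pr(\pi_{\text{DEVICE}} / \pi_{\text{CONTROL}} \geq 1.75) > 0.988". For the risk difference, the null is rejected when the corresponding upper limit for the "difference between the two-year device rate and two-year control rate is less than 2.87" percentage points. The same ratio expression then follows, where a statement about the difference belongs.

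**Accrual (section 2.15.3.6).** Accrual is to stop for predicted success when P(n,n) is at or above S_n. A later sentence reads: "If $F_n \leq P_{n,3000}$ and $P_{n,n} > S_n$, the enrolling of subjects continues".

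**Acute safety.** Four wordings appear.
- Section 2.15.3, item 3: if the "rate is less than 5%, the device is considered to have met the acute safety endpoint".
- Section 2.15.3.4: "the performance goal will be considered met if the upper bound of the one-sided confidence interval for the device rate is less than 5.0" percent, with no confidence level.
- Section 2.15.5.2, opening paragraph: "The endpoint will be considered met if the 96% credible interval for the in-hospital event rate is entirely less than the PG".
- Section 2.15.5.2, after Table 3: "The ACP trial will meet its acute safety success if the two-sided 95% credible interval lies entirely below this PG".

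**Appendix D.** Enrollment stopped at 97 subjects and control subjects leave the trial. The three primary objectives in section 2.15.3 become descriptive summaries, and no labeling claims are intended.

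**The concern.** Taken alone, the probability line in section 2.15.3.2 declares non-inferiority when the posterior is nearly certain that the device is at or beyond the margin. A programmer who coded only that line would pass a clearly worse device and fail an equivalent one. The risk-difference version never mentions 2.87%, although the plan expects most efficacy wins to come through the difference (Scenario 5: 0.925 by difference, 0.384 by ratio). The accrual sentence would keep enrolling exactly when the algorithm says to stop. For acute safety, a primary endpoint with several success criteria invites choosing among them once the data are known. In an open trial heading for a marketing application, each of these would need correcting before the first analysis.

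**Working it through.** **1. Which direction is intended?** A two-sided equal-tailed 97.6% interval leaves (1 − 0.976)/2 = 0.012 in each tail. An upper limit below 1.75 therefore means Pr(ratio < 1.75) > 1 − 0.012 = 0.988, or Pr(ratio ≥ 1.75) < 0.012. The printed line reverses the inequality inside the probability. The other statements of the rule are:

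| Place | Direction |
|---|---|
| 2.15.3.2, hypotheses and interval rules | correct, for ratio and difference |
| 2.15.3.2, two lines claiming equivalence | reversed; the second also names the ratio instead of the difference |
| 2.15.3.2, after the prior and posterior are given | correct, for ratio and difference |
| 2.15.3.3, predictive step | correct, for both |
| 2.15.5.3.3, column definitions and Scenario 5 settings | correct, for both |
| 2.15.9.12, tipping-point analysis | correct, though it writes λ for π |

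The parallel long-term safety rule in 2.15.3.4 is restated correctly: 98.4% gives 1 − 0.016/2 = 0.992.

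**2. Which rule produced Table 5?** The adaptive design was re-simulated with 1,000 trials per scenario. It used the plan's hazards, priors, S_n and F_n bounds, looks every 50 subjects from 400 to 3000, and final analyses at 6, 12, 18 and 24 months. Accrual was 25 per month with 5% yearly dropout. The non-inferiority rules pointed the correct way and accrual stopped when P(n,n) ≥ S_n.

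| Quantity | Plan | Re-simulated |
|---|---|---|
| Scenario 5, efficacy | 0.925 | 0.925 |
| Scenario 5, by ratio | 0.384 | 0.362 |
| Scenario 5, by difference | 0.925 | 0.925 |
| Scenario 5, safety | 0.928 | 0.914 |
| Scenario 5, joint power | 0.914 | 0.911 |
| Scenario 4, type I error | 0.022 | 0.020 |
| Scenario 3, type I error | 0.018 | 0.019 |

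Mean sample size came out lower than stated (Scenario 5: 1743 against 1880; Scenario 4: 1366 against 1919). The plan does not fully specify the predictive step and the re-simulation approximates it, so this does not show the stated sizes to be wrong. The power and error rates agree with the correct direction.

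The reversed line could not have produced them. At a fixed 1880 subjects with the 6-month look, equal two-year rates pass 95.3% of the time under the correct rule and 0% under the reversed one. With a device rate about three times control, chosen for illustration, the figures are 0% and 63%.

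**3. Accrual.** The paragraph with the wrong sign goes on to say that looks recur every 50 subjects until P(n,n) ≥ S_n, P(n,3000) < F_n, or 3000 subjects are reached. That covers the ordinary case P(n,n) < S_n. Section 2.15.3 also stops accrual on a high predictive probability. One sign in one sentence is wrong; no rule is missing.

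**4. Acute safety.** At the plan's mean size for Scenario 5, device subjects number 2/3 × 1880 ≈ 1253. The table gives the largest passing event count and the binomial chance of passing at a true rate of 4.93% (Table 3's literature rate) and 4.0%. Interval limits are exact; a flat prior gives the same counts.

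| Reading | Maximum events | Pass at 4.93% | Pass at 4.0% |
|---|---|---|---|
| Two-sided 96% interval | 46 | 2.0% | 31% |
| Two-sided 95% interval | 47 | 2.8% | 36% |
| One-sided 95% bound (level assumed) | 49 | 5.1% | 47% |
| Observed rate below 5% | 62 | 55% | 96% |

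Under a Jeffreys prior, the 95% and 96% intervals both allow 47 events. Between the two stated levels, the gap is at most one event.

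**The case for a change.** The strongest case for a change is that the slips are real and sit in the sections defining the primary tests. The ratio line is duplicated where a difference belongs, so it is not a scanning fault. Appendix D does not name 2.15.3.2, 2.15.3.6 or 2.15.5, and those headings carry no pointer to it. Correction would cost only wording, and a reader of 2.15.5 alone would not learn that the acute-safety test has gone.

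Part of this stands. The text is inconsistent, and section 2.15.5 lacks a cross-reference. The 96% and 95% levels do conflict within one subsection, neither comes with a prior, and section 2.15.3.4 gives no level.

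Three things limit its weight. Sections 2.15.3.2, 2.15.3.4 and 2.15.3.6 fall under 2.15.3, whose heading does refer to Appendix D, and the appendix withdraws each of the three objectives by content, including acute safety. The large acute-safety contrast (55% against 2% to 5% at a true 4.93%) depends on reading item 3 of the design summary as a point-estimate test. That list states the efficacy goal just as loosely, as a risk ratio below 1.75, while the detailed sections require an interval in both cases. The one-sided bound without a level is incomplete but compatible with either credible-interval statement, so it is not a separate competing rule.

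**Conclusion.** No change to the plan follows. The two reversals are clerical: each is contradicted by correct statements in its own section and elsewhere, and the stated power and type I error are reproduced with the correct rules. An analyst implementing the design would have found only one workable direction. The remaining numerical conflict, 95% against 96% for acute safety, is worth at most one event in about 1,253 device subjects, taking the Scenario 5 mean size and exact, flat-prior or Jeffreys limits.

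The deciding fact is that these rules are no longer used. Enrollment closed at 97, short of the first look at 400, so no predictive probability is due. Control subjects have left, all three primary tests are replaced by descriptive summaries, and no labeling claim is intended. With no pass or fail decision left, there is nothing to choose after the fact, and correcting the sentences would alter no analysis or conclusion. This rests on Appendix D governing as written. If the hypothesis tests were ever reinstated, the wording and the acute-safety level would have to be settled first.
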